11.4 Tests during Study Treatment

Arm A (TAS-118/L-OHP)

- (1) Before initiation of next treatment cycle (Day15) (from Day 14 to Day 18 if not feasible on Day 15)
 - Hematology, serum chemistry, urinalysis, physical examination, AE/SAE assessment, concomitant medications
 - Examination is mandatory on Day1 or the day before starting study treatment specified in this protocol.
- (2) If initiation of next treatment cycle is postponed
 - Hematology, serum chemistry, urinalysis, physical examination, AE/SAE assessment, concomitant medications
 - Every 1 week starting on Day 1 of each treatment cycle (the data may be collected within 7 days before the scheduled date).
- (3) If any of abnormality is suspected (if necessary)
 - Weight, body temperature, blood pressure, ECOG PS, electrocardiography

- (4) Every 6 weeks from the day of randomization (within 1 week before or after the scheduled date)

- Tumor measurement, tumor markers

If PD is strongly suspected by any symptoms or signs, perform extra tumor measurement objectively at the discretion of the investigator (or subinvestigator) even if not the scheduled date.

In case of performing extra tumor measurement, the measurement of the tumor marker is not mandatory.

Arm B (S-1/CDDP) [CDDP on Day1] (Korea)

- (1) Day 15 in each cycle (from Day 8 to Day 22 if not feasible on Day 15)
- Physical examination, hematology, serum chemistry, urinalysis, AE/SAE assessment, concomitant medications
- (2) Before initiation of next treatment cycle (Day36) (from Day 29 to Day 43 if not feasible on Day 36)
- Hematology, serum chemistry, urinalysis, physical examination, AE/SAE assessment, concomitant medications
 - Examination is mandatory on Day1 or the day before starting study treatment specified in this protocol.
- (3) If initiation of next treatment cycle is postponed
- Hematology, serum chemistry, urinalysis, physical examination, AE/SAE assessment, concomitant medications
 - Every 1 week starting on Day 1 of each treatment cycle if the next treatment cycle is delayed (the data may be collected within 7 days before the scheduled date).
- (4) If any of abnormality is suspected (if necessary)
- Weight, body temperature, blood pressure, ECOG PS, electrocardiography
- (5) Every 6 weeks from the day of randomization (within 1 week before or after the scheduled date)
- Tumor measurement, tumor markers

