5.2.1.1.3 Acceptable Time Window

For each evaluation time point, data obtained within the time window specified below will be used. If multiple observations or measurements are available within a time window, data outside the time window will be excluded, and then the data obtained on the day closest to the scheduled day will be used for each parameter of observation or measurement. If measurement days before and after the scheduled day are shifted by the same number of days, the data obtained after the scheduled day will be used.

[Imaging assessment (overall response)] The reference day is the randomization day.

Time point	Scheduled day	Time window
6 weeks after randomization	Day 43	Randomization day \leq measurement day \leq Day 50
$n \times 6$ weeks after randomization	Day ($n \times 42 + 1$)	Day ($n \times 42 - 6$) \leq measurement day \leq Day ($n \times 42 + 8$)

[Sum of diameters of target lesions/laboratory values/tumor markers/vital signs (including height/weight/BSA)]

Time point	Scheduled day	Time window
Baseline	Start date of study treatment	Measurement day \leq start date of study treatment

[Cycles used for the analyses]

Relationship between the start date of treatment in each cycle and the assessment day	Cycle used for the analysis
Start date of treatment in Cycle $x <$ assessment day $<$ start date of treatment in Cycle $x + 1$	Cycle x
Start date of treatment in Cycle $x =$ assessment day and assessed after treatment	Cycle x
Start date of treatment in Cycle $x =$ assessment day and examined before treatment	Cycle $x - 1$ If $x = 1$, then baseline is used.
Start date of treatment in Cycle $x <$ assessment day (with no next cycle) within the cycle decision period*	Cycle x
Start date of treatment in Cycle $x <$ assessment day (with no next cycle) outside the cycle decision period*	After safety follow-up

*Data obtained on the date of the last study treatment + 30 days or the start date of subsequent therapy, whichever comes first (including the day), will be included in the cycle decision period. Data obtained within this period after the date of the last study treatment will be included in the last cycle.

When data are collected in each cycle that is not specified in the list, all cycles except those after safety follow-up will be included in the analysis.

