7.9. Laboratory Values

The following analyses will be conducted in the AT population. These analyses except listings will also be conducted by country. The listings will be based on the enrolled population.

- The change in laboratory values over time from the start of each cycle in each subject will be graphed by treatment arm.
Laboratory values to be evaluated are hemoglobin, white blood cell count, neutrophil count, lymphocyte count, and platelet count.
- The minimum level of laboratory tests at predose and at each cycle in each subject will be identified by treatment arm, the summary statistics will be presented, and the levels will be summarized by grade.
Laboratory tests to be evaluated are hemoglobin, white blood cell count, neutrophil count, lymphocyte count, platelet count, albumin, Na, K, and corrected Ca.
- The maximum level of laboratory tests at predose and at each cycle in each subject will be identified by treatment arm, the summary statistics will be presented, and the levels will be summarized by grade.
Laboratory tests to be evaluated are AST, ALT, ALP, bilirubin, creatinine, Na, K, and corrected Ca.
- The worst level of urine protein at predose and at each cycle in each subject will be identified by treatment arm and summarized by category.
- The minimum level of laboratory tests throughout the study period in each subject will be identified by treatment arm, and the summary statistics will be presented for predose level, minimum level, the number of days to the minimum level, and cycle with the minimum level.
Laboratory tests to be evaluated are hemoglobin, white blood cell count, neutrophil count, and platelet count.
- The summary statistics will be presented for the minimum level of laboratory tests in subjects with grade 3 or higher reduction, the number of days from the start date of onset cycle to the minimum level, and the number of days required for recovery to grade 2 or less from the minimum level within an onset cycle in each treatment arm.
Laboratory tests to be evaluated are hemoglobin, white blood cell count, neutrophil count, and platelet count.
If grade 3 or higher reduction is observed in more than one cycle in the same subject, both decreased levels will be used for calculating the summary statistics.

Subjects who meet any of the following criteria will be regarded as those who are not recovered:

- After grade 3 or higher reduction, grade 2 or less is not measured within the same cycle.

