- Measurement date of grade 2 or less reduction in laboratory values – date of the last study treatment ≥ 30 days

When the start date of subsequent therapy \leq date of the last study treatment + 30 days is met, the following criterion will be used:

Measurement date of grade 2 or less reduction in laboratory values \geq start date of subsequent therapy

- After “grade 3 or higher reduction” is replaced with “grade 2 or higher reduction” and “recovery to grade 2 or less” is replaced with “recovery to grade 1 or less,” the same analyses as specified above will be conducted.

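### SAP 7.9's same-cycle recovery rule makes haemoglobin and WBC recovery, and Grade 2+ neutrophil recovery when L-OHP is skipped, depend on each arm's sampling schedule

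*SAP*

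**What the plan says.** SAP 7.9 summarises, for subjects with a Grade 3 or higher reduction, the minimum value, the days from cycle start to that minimum, and "the number of days required for recovery to grade 2 or less from the minimum level within an onset cycle". On scope it states: "Laboratory tests to be evaluated are hemoglobin, white blood cell count, neutrophil count, and platelet count". A subject is not recovered if "After grade 3 or higher reduction, grade 2 or less is not measured within the same cycle", or if the recovery value comes 30 days or more after the last study treatment or on or after the start of subsequent therapy. For the version that starts at Grade 2 and asks for recovery to Grade 1 or less, "the same analyses as specified above will be conducted".

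SAP 5.2.1.1.3 decides which cycle a sample belongs to. A sample on the start day of Cycle x ("assessment day and examined before treatment") goes to Cycle x−1, and samples between two starts go to the earlier cycle. Samples after the last treatment go to the last cycle, up to and including 30 days or the start of subsequent therapy.

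Scheduled haematology is in Protocol 11.4:

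- Arm A: "Before initiation of next treatment cycle (Day15) (from Day 14 to Day 18 if not feasible on Day 15").
- Arm B, both countries: "Day 15 in each cycle (from Day 8 to Day 22 if not feasible on Day 15"), then Day 36 before the next cycle. Japan adds Day 8.
- Both arms: weekly tests if the next cycle is delayed, and a mandatory test on Day 1 or the day before each start.

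**The concern.** Comparing safety between arms is a secondary objective (Protocol 4.2). A recovery summary by arm is informative only if recovery has a similar chance of being seen in each arm. When an on-schedule Arm A cycle contains a single scheduled value, that value is both the minimum and the last value of the cycle, so nothing scheduled in the cycle can show recovery. The next sample, which may show it, belongs to another cycle and is not used. An Arm B cycle has a later scheduled sample after Day 15.

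For some analytes, then, the proportion not recovered could look worse in Arm A because of when blood was drawn. The by-country tables are exposed as well, since Arm B sampling differs between Japan and Korea. SAP 7.10 sets no same-cycle limit when it summarises recovery of clinical findings from Grade 3 or higher to Grade 2 or less, so the two sections measure recovery differently.

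**Working it through.** The plan states no figure on this point, so there is none to reproduce. The check traces the schedule.

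**Step 1. Which lows hold up the next cycle?** Protocol Tables 10.1.3.1-1 and 10.1.3.1-2 give the start criteria.

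| Analyte | Start criterion | Grade 3+ version (recovery to ≤2) | Grade 2+ version (recovery to ≤1) |
|---|---|---|---|
| Neutrophils | ≥1000/mm³ for TAS-118 or S-1 (≤Grade 2); ≥1500/mm³ for L-OHP or CDDP (≤Grade 1) | held up | Arm A: not held up if L-OHP is skipped |
| Platelets | ≥75000/mm³ (≤Grade 1) | held up | held up |
| Haemoglobin | none | not held up | not held up |
| WBC | none | not held up | not held up |

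Protocol 10.1.2.1 allows a TAS-118-only cycle when the L-OHP criterion fails, so a cycle can start with neutrophils from 1000 to below 1500.

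**Step 2. When is a recovery captured?** Let n be the day the low is first seen, r the day of true recovery, s a sample day, N the start day of the next cycle and L the last oral dose day (Day 7 in Arm A, Day 21 in Arm B). A recovery is captured if some sample satisfies s > n, s ≥ r, s ≤ N (pre-dose) and s − L < 30. Assumptions: nominal sample days, no unscheduled tests, starts as early as the criteria allow, and r running over the 28 days after n.

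**Step 3. Analytes that do not hold up the cycle, next cycle on time.**

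- Arm A: only sample s = 15, N = 15, n = 15. No s satisfies 15 < s ≤ 15. Captured: 0 of 28.
- Arm B, n = 15: s = 36, N = 36. Captured for r = 16 to 36, which is 36 − 16 + 1 = 21 of 28.
- Arm B, n = 36: no later sample in the cycle. Captured: 0 of 28.
- Arm B Japan, n = 8: captured for r = 9 to 36, which is 36 − 9 + 1 = 28 of 28.

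**Step 4. Analytes that hold up the cycle.** In Arm A a Day 15 low delays the start, giving weekly samples on Days 22, 29 and 36. The last of these is within the limit, because 36 − 7 = 29 < 30. Recoveries on r = 16 to 36 are captured: 21 of 28. The other seven (Days 37 to 43) are lost to the stop after more than 28 days off drug (Protocol 13.1.1) and the 30-day limit, not to the same-cycle rule. The sample that releases the next cycle is itself a same-cycle recovery value. The corresponding Arm B counts are 28 of 28 for a Day 15 low and 14 of 28 for a Day 36 low (captured to Day 50, since 50 − 21 = 29).

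**Step 5. Spacing.** Where recovery is captured, its recorded time follows the sampling grid: 7-day steps between re-tests during an Arm A delay, against 36 − 15 = 21 days between the scheduled Arm B samples. The inclusive count of SAP 5.2.1.1.1 adds one day to each.

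The counts out of 28 are possible recovery days given equal weight. They are not estimated probabilities.

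**The case against.** The strongest reply is that the start criteria, the weekly re-tests and the pre-dose assignment protect the counts that govern dosing. That stands for Grade 3+ neutrophils, and for platelets in both versions. A reader might infer that the rule misclassifies any low blood count in Arm A; the documents do not support that.

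The single-sample picture is also not absolute:

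- A Day 14 sample followed by a Day 16 start requires a second test in the same cycle.
- Protocol 15.2.2 asks for repeat testing of clinically significant results as clinically indicated.
- Investigators may postpone a cycle even when all criteria are met, which triggers weekly tests.
- A WBC low accompanied by neutrophils below 1000/mm³ shares the neutrophil delay.
- End-of-treatment samples count in the last cycle.

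All of these stand, and they reduce the number of episodes affected by an amount the documents do not give.

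It can also be said that Arm B loses lows first seen at Day 36, and that the 7-day grid can make Arm A recovery look faster. Both are correct, so the direction is not uniform across the table.

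Finally, SAP 7.9 plans no test between arms. The adverse event tables by grade and the worst values per cycle do not use the recovery rule. To call the whole arm comparison an artefact would go too far. Within-cycle recovery is a coherent measure, but the SAP does not warn that its result depends on the sampling schedule.

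**Conclusion.** The point holds in a limited form. For haemoglobin and WBC in both versions, and for neutrophils in the Grade 2+ version when TAS-118 starts with L-OHP skipped, an Arm A low at the scheduled pre-dose sample is scored not recovered by rule. This applies when the next cycle starts on time and no unscheduled test is done. On scheduled samples alone, 0 of 28 possible recovery days are captured, against 21 of 28 for an Arm B low at Day 15 and 0 of 28 for one first seen at Day 36.

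A reader might conclude that many Arm A recoveries are lost. The documents give no rates of these lows, of delays or of unscheduled tests. The share of these Arm A episodes affected therefore runs from 0% (every next start delayed past recovery, or re-tests done in time) to 100% (all on time, none re-tested). The consequence is confined to a descriptive safety table; no efficacy result depends on it. It is still worth correcting, because the difference comes from the schedule and the data needed are already collected.

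**What to change.** In SAP 7.9, for haemoglobin, WBC and (in the Grade 2+ version) neutrophils:

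1. Take recovery as the first later value at Grade 2 or less (Grade 1 or less in the repeat) in any cycle, up to the limit 7.9 already sets.
2. Define an episode as running from the first low value to that recovery. At present 7.9 uses every affected cycle, so consecutive low cycles would otherwise share one recovery date and be counted twice.
3. If Kaplan-Meier is used, restrict it to the first episode per patient, because repeated episodes in one patient are correlated.
4. Keep the within-cycle version as supplementary.
5. State under the table that days to minimum and days to recovery depend on each arm's sampling days.
6. Reconcile the 30-day edge. SAP 5.2.1.1.3 includes day 30 after the last treatment in the last cycle, while 7.9 scores a recovery at 30 days or more as not recovered. The safety follow-up visit in Protocol 11.6 is nominally on that day.

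The cost is a few lines of SAP text and some programming, with no new data. The downside is that recovery may then span a further treatment cycle and is no longer purely off-drug, which is the reason to keep the within-cycle version alongside. Recovery times will still follow the spacing of samples.

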8.1 Inclusion Criteria

Patients must fulfill all of the following criteria at the time of randomization in this study: The rationale is provided in “26.5 Rationale for inclusion criteria”.

- (1) Histologically confirmed adenocarcinoma of the stomach or esophagogastric junction with metastatic or recurrent disease.
- (2) Measurable or evaluable metastatic lesion(s), according to RECIST version 1.1 detected by CT scan or MRI for response evaluation within 21 days prior to randomization.
- (3) Negative or unknown for HER2 testing.
- (4) No prior treatment (e.g. radiotherapy, chemotherapy, hormonal therapy) for gastric cancer.
 - Adjuvant chemotherapy is permitted if more than 180 days has elapsed between the end of adjuvant therapy and first recurrence. Adjuvant chemotherapy with platinum agent is not permitted.
- (5) ECOG PS of 0 to 1.
- (6) At least 20 years of age^{*1} at the time of informed consent.
- (7) The following bone marrow, liver, and kidney function parameters measured within 14 days prior to randomization:
 - 1) Neutrophil count $\geq 1500/\text{mm}^3$ ^{*2}
 - 2) Hemoglobin ≥ 8.0 g/dL^{*2}
 - 3) Platelet count $\geq 100000/\text{mm}^3$ ^{*2}
 - 4) Total bilirubin ≤ 1.5 mg/dL
 - 5) AST, ALT levels ≤ 3 x ULN, or ≤ 5 x ULN in the presence of liver metastasis
 - 6) ALP levels ≤ 2.5 x ULN, or ≤ 5 x ULN in the presence of liver metastasis
 - 7) Creatinine clearance ≥ 60 mL/min^{*3}
- (8) Life expectancy of at least 90 days after randomization.
- (9) Capable of oral intake.
- (10) Written informed consent to participate as a subject in this clinical study.

^{1*} : For 75 years of age or older patient, pay careful attention to manage adverse events.

^{2*} : If patients received blood transfusion or treatment with any blood product or hematopoietic factor such as G-CSF, it must be confirmed the data is obtained more than 14 days after the last blood transfusion or treatment.

^{3*} : A value obtained from a urine collection, if available. Otherwise an estimate by the Cockcroft-Gault formula:

Estimated creatinine clearance (mL/min)
= $(140 - \text{age}) \times \text{Body weight (kg)} / [72 \times \text{Serum creatinine (mg/dL)}]$
For women, the obtained value is multiplied by a factor of 0.85.

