10.1.3 Criteria for Modification of Treatment Schedule

10.1.3.1 Criteria for Dose Initiation in Each Cycle

Cycle 1 will be started after completion of the scheduled examination and the confirmation of being met all of dose initiation criteria in each cycle (Table 10.1.3.1-1, Table 10.1.3.1-2), which may be substituted by the test at randomization performed within 7 days prior to Day 1 treatment start. Cycle 2 and later cycles will be started if the results of the scheduled examination on or one day before Day 1 meet all the following criteria (Table 10.1.3.1-1, Table 10.1.3.1-2). No treatment cycle can be started if any of these criteria are not met. Even if a subject meets all the following criteria, dose initiation can be postponed at the investigator's discretion. Even if all of dose initiation criteria were met, administration of L-OHP or CDDP may be skipped and each treatment cycle can be started only with TAS-118 or S-1 at the investigator's discretion.

Table 10.1.3.1-1 Dose initiation criteria in each cycle for TAS-118 and L-OHP (Arm A)

Item	TAS-118	L-OHP
Neutrophil count	$\geq 1000 /\text{mm}^3$ (\leq Grade2) *1	$\geq 1500 /\text{mm}^3$ (\leq Grade1) *1
Platelet count	$\geq 75000 /\text{mm}^3$ (\leq Grade1) *2	
Serum creatinine*3	$< 1.5 \text{ mg/dL}$ (1.2 - $< 1.5 \text{ mg/dL}$: 1 level down)	-
Infection	No infection with fever ($< 38^\circ\text{C}$)	
Diarrhea, Stomatitis, Anorexia	\leq Grade1	
Peripheral sensory neuropathy	-	\leq Grade2*4

*1 : If the patients received G-CSF, it must be confirmed the data is obtained more than 48 hours after the last administration.

*2 : If the patients received platelet transfusion, it must be confirmed the data is obtained more than 48 hours after the last transfusion.

*3 : New treatment cycle would be initiated with creatinine clearance $\geq 50 \text{ mL/min}$, as a reference.

*4 : Even if the grade is ≤ 2 , administration of L-OHP may be skipped at the investigator's discretion.

Table 10.1.3.1-2 Dose initiation criteria in each cycle for S-1 and CDDP (Arm B)

Item	S-1	CDDP
Neutrophil count	$\geq 1000 /\text{mm}^3$ (\leq Grade2)*1	$\geq 1500 /\text{mm}^3$ (\leq Grade1)*1
Platelet count	$\geq 75000 /\text{mm}^3$ (\leq Grade1)*2	
Serum Creatinine*3	$< 1.5 \text{ mg/dL}$ (1.2 - $< 1.5 \text{ mg/dL}$: 1 level down)	$< 1.5 \text{ mg/dL}$ (1.2 - $< 1.5 \text{ mg/dL}$: 10 mg/mm^2 reduction from previous cycle)
Infection	No infection with fever ($< 38^\circ\text{C}$)	

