15.2 Laboratory Evaluations

15.2.1 Reporting and Evaluation of Laboratory Test Results

Laboratory tests are to be performed as required per protocol. All laboratory values that are out of the normal range are to be evaluated for their clinical significance before exposing the patient to the next dose of study medication.

The laboratory must provide normal reference ranges.

Any laboratory abnormality that is clinically significant, e.g., results in delay of study

medication dosing, study discontinuation, requires treatment due to abnormal values, or is considered by the investigator to be medical important, must be reported as an AE, unless it is considered a supporting lab to a clinical diagnosis that is already reported as an AE. All laboratory data will be analyzed using NCI CTCAE grade criteria (version 4.03).

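### The Grade 2 rerun of the blood-count recovery analysis (SAP 7.9) moves the recovery endpoint to Grade 1 but leaves the three non-recovery criteria at Grade 2

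*SAP*

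**What the plan says.** SAP 7.9 covers haemoglobin, white cells, neutrophils and platelets in the AT population. For subjects with a Grade 3 or worse reduction it summarises the lowest value, the days from the start of the cycle to that value, and "the number of days required for recovery to grade 2 or less from the minimum level within an onset cycle". If this happens in more than one cycle, "both decreased levels will be used for calculating the summary statistics".

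It then says who counts as not recovered. The first criterion is "After grade 3 or higher reduction, grade 2 or less is not measured within the same cycle". The second sets a limit of 30 days after the last study treatment. The third replaces that limit when subsequent therapy starts early. Both of these are built on "Measurement date of grade 2 or less reduction in laboratory values".

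The last bullet of the section reruns the analysis one grade lower. The onset phrase moves from Grade 3 to Grade 2, and the recovery phrase "is replaced with “recovery to grade 1 or less,” the same analyses as specified above will be conducted". No other wording changes. The section has no rule for subjects who are already at the onset grade before dosing.

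Protocol 8.1 admits patients with "Hemoglobin ≥ 8.0 g/dL". Protocol 15.2.1 grades laboratory data by CTCAE 4.03. Neither document prints the haemoglobin grade limits.

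**The concern.** Recovery and non-recovery should be complements: a subject in the analysis either has a recovery date or is classed as not recovered. In the Grade 3 version they are, because both use Grade 2 or less. In the rerun the recovery endpoint tightens to Grade 1 or less while the non-recovery test stays where it was. Subjects who remain at Grade 2 then fall between the two definitions.

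This state can be expected to occur. By the labels in the dose-initiation and interruption tables of Protocol 10.1.3, neutrophils from 1000 to below 1500/mm³ are Grade 2. The same tables let TAS-118 or S-1 start a new cycle at 1000/mm³ or more.

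At stake is whether the rerun's non-recovery classification means the same thing in both arms, given that the arms are sampled at different frequencies.

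**Working it through.** No figure in the plan bears on this point, so the check is on wording and classification.

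**Step 1. Apply the swap literally to each line of SAP 7.9.**

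| Line | Changed by the swap? | Threshold in the rerun |
|---|---|---|
| Days to recovery | yes, onset and recovery | recovery at Grade 1 or less |
| Use of repeat cycles | yes, onset | none involved |
| Non-recovery 1 (same cycle) | onset only | still Grade 2 or less |
| Non-recovery 2 (30 days) | no | still Grade 2 or less |
| Non-recovery 3 (subsequent therapy) | no | still Grade 2 or less |

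The recovery phrase is swapped as a whole. The non-recovery lines mention Grade 2 or less without the words *recovery to* in front, so the swap does not reach them.

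**Step 2. Classify short sequences of grades within one cycle under the rerun.** The literal rule tests non-recovery at Grade 2 or less. The aligned rule tests it at Grade 1 or less. Recovery needs Grade 1 or less under both.

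| Grades in the cycle | Recovery date | Not recovered, literal | Not recovered, aligned |
|---|---|---|---|
| 2, 2, 2 | none | no | yes |
| 3, 2, 2 | none | no | yes |
| 2, 1 | yes | no | no |
| 3, 1 | yes | no | no |
| 3, 3 | none | yes | yes |
| 2 (no later sample) | none | yes | yes |

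The rules differ only where a later sample in the same cycle is at Grade 2 and none reaches Grade 1.

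**Step 3. Count scheduled samples per cycle by arm (Protocol 11.4; SAP 5.2.1.1.3).** A sample taken before treatment on a cycle's first day belongs to the cycle just ended, or to baseline for Cycle 1. With no delay and no unscheduled samples:

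- Arm A: Day 15, one sample. A steady Grade 2 gives the sequence 2 and is classed as not recovered.
- Arm B, Korea: Day 15 and Day 36. The sequence is 2, 2, which is not classed as not recovered and has no recovery date.
- Arm B, Japan: Day 8, Day 15 and Day 36. The sequence is 2, 2, 2, with the same result as Korea.

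Two situations give Arm A more than one sample. A delayed cycle brings weekly tests. In the last cycle, end-of-treatment and follow-up samples up to 30 days after the last treatment, or to the start of subsequent therapy if earlier, are assigned to that cycle.

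**Step 4. Predose grade.** Entry requires neutrophils of at least 1500/mm³ and platelets of at least 100000/mm³. The protocol's tables label at least 1500 and at least 75000 respectively as Grade 1 or less, so neither count can be Grade 2 at screening. Haemoglobin is admitted from 8.0 g/dL. Write H for the boundary between Grades 1 and 2. If H is above 8.0, entrants from 8.0 up to H are already Grade 2 before any dose; if H is 8.0 or lower, none are. The documents do not give H. White cells have neither an entry limit nor printed grade limits, so the documents settle nothing for them.

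**The case against.** The strongest reply is that the intent is plain. The rerun orders the same analyses with recovery at Grade 1, so a sensible programmer would move the non-recovery lines too. That is fair, and it is why the point is minor. But the SAP prescribes an exact substitution, and followed exactly it gives the wrong class.

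It is also fair that the affected subjects are left unclassified and are not counted as recovered. A reader might infer that a reported non-recovery rate will be too low. The documents do not go that far: SAP 7.9 names no count or proportion of non-recovered subjects, and the lowest value, days to it and days to recovery are unchanged for these subjects. The 30-day and subsequent-therapy lines add little, because SAP 5.2.1.1.3 already places later samples outside the last cycle; only the boundary day differs. The weight rests on the first criterion.

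On haemoglobin, a reader might infer that the rows will be filled with patients wrongly shown as harmed by the drug. The documents do not support this. SAP 7.9 attributes no cause, and neither document gives a grade limit or a haemoglobin distribution, so no share of patients can be stated. Terms such as *reduction* and *onset cycle* could be read as requiring a worsening. Against that, the SAP also uses *reduction* for the recovered value, which suggests a graded level. Predose levels are summarised beside the minimum, and individual profiles are graphed, but neither output separates recovery times by predose grade.

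**Conclusion.** The rerun's non-recovery criteria are wrong as written. All three keep a threshold that contradicts the new recovery endpoint, and subjects who stay at Grade 2 over two or more samples in a cycle are neither recovered nor not recovered. On scheduled samples without delay, outside the last cycle, this happens in Arm B and not in Arm A. How many subjects this involves cannot be derived from the documents.

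The haemoglobin point is conditional. If the CTCAE 4.03 Grade 2 range starts above 8.0 g/dL (an assumption), subjects already at Grade 2 before dosing can enter the rerun without any fall and would have to rise above their entry grade to recover.

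The analysis is a descriptive safety summary. OS, alpha and power are unaffected. Severity: minor.

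**What to change.** In the last bullet of SAP 7.9, state that for the rerun the threshold in all three non-recovery criteria also becomes Grade 1 or less. This is one sentence, with no new data and no change to the Grade 3 version. It makes a steady Grade 2 count as not recovered in both arms. It does not remove the difference in sampling frequency: a single end-of-cycle sample in Arm A cannot show recovery within the cycle, and a table note should say so.

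For haemoglobin, add rows restricted to subjects with predose Grade 1 or less and keep the all-subject rows. This costs one more sentence and one merge with the predose value. Do not replace the all-subject rows with a rule that requires a grade worse than predose: that would drop real falls that stay within one grade.
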